## **REVISION HISTORY**

Revision #	Version Date	Summary of Changes	Consent Change?
1	July 2, 2021	Responding to reviewer comments	AL
2	August 14, 2021	Follow-up date changed to 3-10 days	AL

# 1.0 Study Summary

Study Title	Antibiotic concentration after delivery to middle ear for				
	chronic suppurative otitis media				
Study Design	Prospective observational study				
Primary Objective	Investigate the reliability of ciprofloxacin concentration				
	measurements from aspirates of middle ear fluid after self-				
	administration of otic drops in patients with chronic otorrhea				
	and non-intact tympanic membrane				
Secondary	Elucidate the role of antibiotic concentration in varying				
Objective(s)	clinical outcomes in patients with chronic middle ear				
	infections by using antibiotic concentration analysis of				
	aspirates.				
Research	Patients diagnosed with chronic suppurative otitis media				
Intervention(s)/	prescribed with antibiotic drops $(0.3\%$ ciprofloxacin, 0.1%				
Investigational	dexamethasone suspension) will apply drops 1-hour prior to				
Agent(s)	visit. During visit, the ear will be cleaned of any debris and a				
	microscopic aspirate of approximately 100 microliters will				
	be collected with a modified Juhn Tym-Tap device.				
IND/IDE #	N/A				
Study Population	Adults in the community with diagnosed chronic middle ear				
	infection				
Sample Size	N=10				
Study Duration for	An individual participant will be followed on a weekly basis				
individual	until reaching either criteria of complete symptom				
participants	resolution, new treatment prescription, or maximum duration				
	of 3 months				
Study Specific	Chronic suppurative otitis media (CSOM)				
Abbreviations/					
Definitions					

# 2.0 Objectives\*

The purpose of this study is to develop methodology to better understand the potential effect of ototopical concentration on clinical outcomes in patients with chronic middle ear infections. The investigators will do so by measuring antibiotic concentration in aspirates from the middle ear of selected subjects with otorrhea due to Chronic Suppurative Otitis Media (CSOM) who are prescribed and instructed to self-administer ototopical ciprofloxacin.

The primary specific aim of the study team is to investigate the reliability of measuring the concentration of ciprofloxacin from aspirates of middle ear fluid after self-administration of otic drops in subjects with chronic otorrhea. A secondary aim is to correlate these concentrations with subject factors such as the extent of otorrhea and the anatomy of the ear.

The investigators hypothesize that patient self-administration of ciprofloxacin drops results in variable concentrations delivered to the tissue level that are significantly below the in vitro concentration of the prescribed solution and that these concentrations are below the bactericidal concentration of ciprofloxacin-resistant bacteria as determine by our previous work. Additionally, the investigators anticipate that the concentration levels of ciprofloxacin at the level of the tympanic membrane will correlate with specific patient factors and clinical outcomes.

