To further investigate these relationships, the study team examined the actual MIC and minimal bactericidal concentrations (MBC). In this study, Trinh et al. found that the actual MIC and MBC of ciprofloxacin-resistant ear pathogens are much higher than the plasma-derived MIC levels used to assign resistance, but generally still below the concentration of the ototopical solution (12). This study suggests elevated MIC or MBC levels alone do not explain the observed poor clinical outcomes in patients with ciprofloxacin-resistant infections. These findings have led to the hypothesis that poor clinical outcomes in fluoroquinolone resistance are due to multiple effects, including elevated MICs and poor drug delivery with failure to reach the necessary concentration at the tissue level (tympanic membrane or middle ear).

The potential role of ineffective ototopical delivery of fluoroquinolones and antibiotic resistance in patient outcomes has yet to be elucidated. As such, it is becoming increasingly clear that topical antibiotic delivery is more complex than previously considered. Understanding the complexities of drug delivery is critical to improving patient management and clinical outcomes. Only one study has reported on drug concentration of ototopical solutions at the level of the middle ear. Ohyama et al. studied clinician-administered ototopical fluoroquinolone after ear cleaning using high performance liquid chromatography to measure intratympanic ciprofloxacin concentration. This study demonstrated that commercially available preparations of of loxacin (3000 mcg/ml) resulted in highly variable concentrations (1.2 to 602 mcg/g) in the middle ear mucosa in 11 patients, with undetectable levels in another five patients (13). These results allude to the variety of patient factors that can influence drug penetration and the availability in the middle ear, including volume of otorrhea, the narrowness of the ear canal, differences in surface tension affecting fluid dynamics, and size of the tympanic membrane. These patient related factors are ill defined within the literature and the magnitude of such individual effects is largely unknown. Furthermore, the delivery method employed in this prior study was not consistent with standard medical practice of patient self-administration. As such, the investigators are pressed to further examine the fundamentals of ototopical antibiotic delivery.

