# 5.0 Study Intervention/Investigational Agent

The standard of care for CSOM involves ototopical quinolone therapy such as ciprofloxacin or ofloxacin. The affected ear is routinely cleaned of any debris, and a Juhn Tym-Tap® device will be used to aspirate fluid for culture samples. The patient will be provided the standard course of treatment, which is a prescription

for antibiotic drops of ciprofloxacin 0.3% and dexamethasone 0.1% suspension with specific written instructions. The frequency of treatment is three times daily for ten days.

For this study, patients who meet inclusion-exclusion criteria will be offered an opportunity to participate by the prescribing provider. Informed consent will be obtained. Enrolled subjects will be asked to return 3 to 10 days after the initial visit. Additionally, the subject will be asked to keep a log of their medication use and to administer the ototopical medication one hour prior to their appointment. During the follow-up appointment, the ear will be cleaned of any wax or purulent debris. A microscopic aspirate (~100 µL) will then be collected of fluid at the level of the non-intact tympanic membrane will be collected using with a modified Juhn Tym-Tap®. This type of sampling of middle ear aspirates is commonly performed in the ENT clinic (performed more than 120 times in the Dartmouth-Hitchcock ENT clinic in the past year). After sampling, the volume of the aspirate will then be precisely measured with a device developed specifically for this study. The color and consistency of the sample will be noted. The sample will then be diluted with a known volume of water to an acceptable volume for the LC-MS/MS assay. Furthermore, other data beyond ciprofloxacin concentration such as otologic diagnosis, bacteria culture results, presenting symptoms, specific site of infection, external ear canal volume estimates (based upon tympanometry and physical exam), configuration of external auditory canal, prescribed treatment, treatment outcome, and duration of infection will be noted for each subject.

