## 6.0 Procedures Involved\*

Specimen collection: This will be a prospective observational study of adult subjects being diagnosed with chronic otorrhea at a tertiary care hospital, Dartmouth-Hitchcock Medical Center. To test our hypothesis, we will identify subjects with chronic otorrhea in clinic. Informed consent will be obtained. Subjects will be given a prescription for antibiotic drops containing ciprofloxacin 0.3% and dexamethasone 0.1% suspension from a pharmacy of their choice with specific written instructions for self-administration. A compliance card will be given to record adherence to three-time daily regiment for ten days. Drops will be dosed three times daily for ten days, and no other non-prescribed ototopical antibiotic therapy nor additional over the counter treatments should be used during this period. Subjects will return for a follow up visit between 3 to 10 days after their initial visit and will be asked to administer the drops in the affected ear one hour prior to their appointment. At that time, the ear will once again be cleaned of any debris and a microscopic aspirate (~100  $\mu$ L) of fluid at the level of the tympanic membrane or middle ear will be collected using an aseptic technique with a Juhn Tym-Tap specimen trap to collect micro aspirates. This specimen will be analyzed, precisely measured for

volume, diluted, and sent for analysis using mass spectrometry (description below). Data collected will include patient demographics, otologic diagnosis, bacteria culture results, presenting symptoms, amount and type of drainage, specific site of infection, external ear canal volume estimates, configuration of the external auditory canal based on physical exam, prescribed treatment, treatment outcome, and duration of infection.

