Ciprofloxacin concentration measurements: A reverse-phase liquid chromatography with tandem mass spectrometry (LC-MS/MS) assay will be developed to measure concentrations of ciprofloxacin in the auricular aspirate. The assay is based on that published by Matta et al (16). In brief, a C18 stationary phase column will be used with a gradient elution of 5mM ammonium formate in 0.1% formic acid buffer and acetonitrile for the mobile phase. External standards using a ciprofloxacin stock solution at low, medium, and high concentrations will be used to create a calibration curve of instrument response to known concentrations. For sample analysis, a 30-µL aliquot of the auricular aspirate sample will be combined with a 60-µL water and 100-µL acetonitrile, which would be spiked with a single standardized amount of the internal standard, deuterated 8 ciprofloxacin. By using this internal standard method of calibration, a precise quantification of the ciprofloxacin concentration in the auricular aspirate will be developed and validated by the staff of the Clinical Pharmacology Shared Resource directed by [name].

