## 14.0 Withdrawal of Subjects\*

Circumstances for subject withdrawal from research may include non-compliance with prescribed antibiotic regiment or any additional necessary medical intervention beyond that prescribed for CSOM. The study team does not plan to collect survival data from subjects that withdraw from the study. The subject always has the option to voluntarily withdraw from the study.

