# 17.0 Data Management\* and Confidentiality

Given the small sample size (n=10) and expected variability of results, a Fisher's exact test will be used to describe and compare the measured concentration of ciprofloxacin at the tympanic membrane to subject demographics as well as extent of perforation, amount of aural drainage and treatment outcomes.

The data will be managed on a locally encrypted device in an Excel file while stored on the encrypted cloud storage service called ShareFile. Access will be provided to those on the research team on a need-to-know basis with particular caution to ensure separation of identifiers and data. Any communication in a non-encrypted platform will not contain any protected health information.

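### Does the threshold hypothesis in section 2.0 need its own planned analysis and a bactericidal reference value fixed in advance?

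*Combined protocol and SAP*

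**What the plan says.** Section 2.0 expects delivered concentrations to be variable, "significantly below the in vitro concentration of the prescribed solution and that these concentrations are below the bactericidal concentration of ciprofloxacin-resistant bacteria". It ties the bactericidal part to the team's previous work. The next sentence adds an expected correlation with patient factors and clinical outcomes. Section 6.0 opens its account of specimen collection with "To test our hypothesis, we will identify subjects with chronic otorrhea in clinic".

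The one statistical method is in section 17.0: "a Fisher's exact test will be used to describe and compare the measured concentration of ciprofloxacin at the tympanic membrane to subject demographics", and also to extent of perforation, drainage and treatment outcome. The endpoint table in section 4.0 has two rows: sampling and assay performance, and correlation of concentration with subject factors and outcomes. Neither row compares a concentration with the drop solution or with a minimal bactericidal concentration (MBC).

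On the reference values, section 5.0 specifies a prescription "for antibiotic drops of ciprofloxacin 0.3% and dexamethasone 0.1% suspension with specific written instructions", and section 3.0 puts topical preparations at 3000 mcg/mL. Section 3.0 describes the MBCs of resistant ear pathogens only in words: much higher than the plasma-derived levels used to assign resistance, but "generally still below the concentration of the ototopical solution". The reference list shows that study as accepted for publication.

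**The concern.** A stated hypothesis normally has a matching analysis. Here two parts of it have none: Fisher's test sets subjects against each other and never against 3000 mcg/mL or an MBC.

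The bactericidal part looks the more exposed. A study of several pathogens yields several MBCs, and the plan does not say whether the lowest, a median, the highest or an organism-matched value is meant. A concentration well under 3000 mcg/mL may lie above one MBC and below another. With no rule, the reference could be picked after the concentrations are known, and the report could then say that delivery falls short, or does not, according to that choice. Nor is there a rule for counting an undetectable result. At stake is the study's reading of its own explanation for treatment failure, namely that too little drug reaches the tissue.

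**Working it through.** **1. The solution reference.** 0.3% w/v is 0.3 g per 100 mL = 3 mg/mL = 3000 mcg/mL, which agrees with section 3.0. This comparator leaves no choice open. The highest value in the one earlier concentration study that section 3.0 describes (ofloxacin, clinician-administered, mucosa) was 602 mcg/g. Treating mcg/g as mcg/mL (an assumption), 602/3000 = 20% of solution strength. If all ten subjects fell below 3000, even a simple exact sign test would give a two-sided p of 2 × 0.5^10 = 0.002, and nine of ten would give 2 × (10 + 1) × 0.5^10 = 0.021. A reader with the ten values can see the answer without a pre-written test.

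**2. The bactericidal reference.** No MBC figure, summary statistic or matching rule appears anywhere in the document. Only the source is fixed: the team's own earlier study, whose results predate this one. The team can choose among those MBCs but cannot alter them.

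**3. Could the choice matter?** The documents do not allow this to be calculated, so what follows is illustration only. Assume the earlier ofloxacin spread applies: 5 of 16 undetectable, and the other 11 of 16 log-uniform from 1.2 to 602. Assume also that candidate MBCs run from 16 to 1024 mcg/mL. The expected share below a reference t (capped at 100%) is

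5/16 + (11/16) × ln(t/1.2) / ln(602/1.2).

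| Assumed MBC (mcg/mL) | Expected share below |
|---|---|
| 16 | 60% |
| 64 | 75% |
| 256 | 91% |
| 1024 | 100% |

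So the choice could matter if the true MBCs spread that widely. Nothing in the documents says that they do.

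**4. What ten subjects can show for any reference.** Exact (Clopper-Pearson) 95% intervals; for 10/10 the lower limit is 0.025^(1/10) = 0.692.

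| Below the reference | 95% interval |
|---|---|
| 10/10 | 69% to 100% |
| 9/10 | 55% to 99.7% |
| 8/10 | 44% to 97% |
| 5/10 | 19% to 81% |

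These hold for any proportion at this sample size and do not measure the harm from an unnamed MBC. They do show that neighbouring results overlap heavily, so the threshold comparison could only ever be descriptive.

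**5. Undetectable results.** Section 6.0 mixes 30 µL of sample with 60 µL of water and 100 µL of acetonitrile: (30 + 60 + 100)/30 = 6.3-fold. Section 5.0 says "The sample will then be diluted with a known volume of water to an acceptable volume for the LC-MS/MS assay". If that is a separate step of 1- to 10-fold (assumed), the total is 6.3- to 63-fold. But it may be the same water step as in section 6.0. The factor also raises the limit on the aspirate scale only if the limit is stated for the injected mixture; if the calibration standards go through the same preparation, it is already included. The plan gives neither a detection limit nor an MBC, so nothing shows that the first would come near the second.

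**6. Place in the study.** Set beside section 4.0, the two unanalysed parts correspond to no endpoint. The primary aim, reliability of measurement, does not depend on them. The correlation sentence of section 2.0 is the part that section 17.0 does analyse.

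**The case for a change.** The best case for a change is that the bactericidal comparison bears most directly on the study's rationale. Section 3.0 attributes poor outcomes partly to drug failing to reach the necessary concentration at the tissue. It also reports earlier values spanning about 500-fold (602/1.2 = 502), with 5 of 16 patients undetectable, so both an open threshold and a need to handle undetectable results were foreseeable. The remedy would be cheap: a few sentences, using MBCs already measured, with no added subjects or visits.

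Part of this stands. Neither threshold statement has a planned summary, and a reference named before the assays were read would make the report easier to trust. What does not stand is the step from an unwritten detail to a defect. No rule in the plan gives a wrong result, and no figure in it shows that the choice of MBC or a detection limit would change the conclusion. The chance of after-the-fact selection is inferred from silence and bounded by a finished study. A fuller rule is also less simple than it looks: ranking every undetectable result lowest can fail if detection limits differ between subjects, because a sample with a high limit need not lie below another subject's low measured value.

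**Conclusion.** The observation is correct for the two threshold statements in section 2.0 and does not extend to the correlation statement or the primary aim. It is missing detail in a ten-subject observational methods study, and analysts would ordinarily fill it: list the ten concentrations beside 3000 mcg/mL and beside the team's own published MBCs, say which MBCs were used, and show undetectable results as such with their limits. With all values listed, a reader can apply any MBC, so a selective choice would be visible.

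The size of the problem cannot be established from the documents. Each subject who changes side moves the proportion by 10 points, but how many would do so rests on MBCs that are not given. The conclusion assumes that the individual concentrations are reported, which is the natural course with ten subjects, and that the bactericidal claim is presented as description. A report resting a firm inferential claim on one unexplained MBC would deserve challenge then; the plan as written does not require amendment.

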# 3.0 Background\*

Chronic suppurative otitis media (CSOM) is characterized by chronic inflammation of the middle ear with persistent discharge from a non-intact tympanic membrane. CSOM is notably associated with a significant burden of disease worldwide (1). The most common pathogens are staphylococcus spp., klebsiella spp., pseudomonas aeruginosa, corynebacterium spp, and proteus spp. (2). Topical fluoroquinolones are first line therapy for CSOM and are advantageous as compared to oral or intravenous therapy in that these antibiotics avoid systemic side effects and have the potential to deliver high antibiotic concentrations directly to the middle ear mucosa (3-5). However, because of their widespread use, fluoroquinolone resistance has steadily risen (6-8), making management of CSOM challenging.

A prior study by the study team confirmed 141 patients with ciprofloxacin-resistant otitis media had poor outcomes when using ciprofloxacin drops compared to alternative therapy options (9). Similarly, Jang et al. recovered ciprofloxacin-resistant P. aeruginosa from all patients (n=88) with unremitting CSOM in the context of topical ciprofloxacin therapy in a prospective population of 231 outpatients. Of these 88, over 40% required intravenous antibiotics (10). These findings contradict the previously accepted thought by many practicing otolaryngologists that the high concentrations (3000 mcg/ml) obtained with topical fluoroquinolone antibiotic preparations (3000 mcg/ml) would sufficiently

overcome all bacterial resistance to fluoroquinolones. This belief is based on the fact that minimum inhibitory concentration (MIC) levels are derived from available plasma concentrations. (4,11).

To further investigate these relationships, the study team examined the actual MIC and minimal bactericidal concentrations (MBC). In this study, Trinh et al. found that the actual MIC and MBC of ciprofloxacin-resistant ear pathogens are much higher than the plasma-derived MIC levels used to assign resistance, but generally still below the concentration of the ototopical solution (12). This study suggests elevated MIC or MBC levels alone do not explain the observed poor clinical outcomes in patients with ciprofloxacin-resistant infections. These findings have led to the hypothesis that poor clinical outcomes in fluoroquinolone resistance are due to multiple effects, including elevated MICs and poor drug delivery with failure to reach the necessary concentration at the tissue level (tympanic membrane or middle ear).

The potential role of ineffective ototopical delivery of fluoroquinolones and antibiotic resistance in patient outcomes has yet to be elucidated. As such, it is becoming increasingly clear that topical antibiotic delivery is more complex than previously considered. Understanding the complexities of drug delivery is critical to improving patient management and clinical outcomes. Only one study has reported on drug concentration of ototopical solutions at the level of the middle ear. Ohyama et al. studied clinician-administered ototopical fluoroquinolone after ear cleaning using high performance liquid chromatography to measure intratympanic ciprofloxacin concentration. This study demonstrated that commercially available preparations of of loxacin (3000 mcg/ml) resulted in highly variable concentrations (1.2 to 602 mcg/g) in the middle ear mucosa in 11 patients, with undetectable levels in another five patients (13). These results allude to the variety of patient factors that can influence drug penetration and the availability in the middle ear, including volume of otorrhea, the narrowness of the ear canal, differences in surface tension affecting fluid dynamics, and size of the tympanic membrane. These patient related factors are ill defined within the literature and the magnitude of such individual effects is largely unknown. Furthermore, the delivery method employed in this prior study was not consistent with standard medical practice of patient self-administration. As such, the investigators are pressed to further examine the fundamentals of ototopical antibiotic delivery.

